## 4. ANALYSIS VARIABLES

# 4.1. Demographic and Baseline Characteristics

For each patient, demographic and baseline characteristics will be obtained from the last available value up to the date of the first double blind study treatment administration (ie, baseline definition).

All baseline safety and efficacy parameters (apart from those listed below) will be presented along with the summary statistics in the safety and efficacy sections. The following variables will be summarized:

Regeneron Pharmaceuticals, Inc.

Page 18 of 88

# Demographic Characteristics

- Sex (Male, Female)
- Race (White, Black or African American, Asian, American Indian or Alaska Native, Native Hawaiian or other, Pacific Islander, Not Reported, Other)

Protocol: R4461-PLD-20100

Date: May 16, 2024

- Age in years (quantitative and qualitative variable:  $\ge 18$  to <45,  $\ge 45$  to <65,  $\ge 65$  to <75, and  $\ge 75$  years)
- Ethnicity (Hispanic or Latino, Not Hispanic or Latino, Not reported, Unknown)

#### **Baseline Characteristics**

- Baseline Weight (kg)
- Baseline Height (cm)
- Baseline Body mass index (BMI) in kg/m^2 (quantitative and qualitative variable defined as  $<30, \ge 30$ )
- Leptin by sex (leptin in male, leptin in female)
- Strata on leptin
  - Randomization strata as reported in the IVRS, leptin (≤ 8mg/dL or 8 mg/dL to 20 mg/dL)
  - Actual strata as reported in the clinical database, leptin (≤ 8mg/dL or 8 mg/dL to 20 mg/dL)
- Baseline Disease Characteristics
- Fasting TG in mg/dL quantitative variable and qualitative variable defined as: >200 to ≤450, and >450)
- HbA1c (quantitative variable)
- Strata on screening HbA1c
  - Randomization strata as reported in the IVRS, screening HbA1c (≤7% or >7%)
  - Actual strata as reported in the clinical database, screening HbA1c ( $\leq 7\%$  or  $\geq 7\%$ )
- Fasting glucose
- Liver volume from MRI and liver fat content from MRI-PDFF
- Insulin (quantitative variable and qualitative variable defined as: Yes/No)
- Lipid Panel
  - Low density lipoprotein cholesterol (LDL-C)
  - High-density lipoprotein cholesterol (HDL-C)
  - Total Cholesterol (TC)
  - Apolipoprotein B

## Regeneron Pharmaceuticals, Inc.

• Biomarker-Lipoprotein NMR Analysis (Note: List of data fields reported in the biomarker-lipoprotein NMR are listed in Appendix 10.5.)

Protocol: R4461-PLD-20100

Date: May 16, 2024

- Body Composition from DXA
  - Total lean mass
  - Total fat mass
  - Trunk fat mass
  - Percentage of body fat
  - Trunk/leg fat ratio (TLR; trunk fat %/leg fat %)

# 4.2. Medical History

As applicable, patient medical history will be dictionary coded by primary system organ class, high level term, and preferred term using the Medical Dictionary for Regulatory Activities (MedDRA), specifically the latest MedDRA version at the time of the first database lock.

FPLD disease history will be assessed by the following variables:

- FPLD related medical history (Yes/No)
- Time from diagnosis to study treatment randomization (years)
- FPLD type
- Genetic variant known (Yes/No): if yes, then list.
- Pathogenic variant as determined by ClinVar (Yes/No)
- Method of diagnosis of FPLD

## 4.3. Prior and Concomitant Medications

All medications taken from the time of informed consent to the final study visit, including medications that were started before the study and are ongoing during the study, will be reported in Concomitant Medications CRF.

All medications will be dictionary coded using the World Health Organization-Drug Dictionary (WHO-DD) to both an anatomic category and a therapeutic category, with the latest version at the time of the first database lock. Drug names will be matched to respective Anatomical-Therapeutic-Chemical (ATC) classification, although a drug can be matched to more than one ATC classification (ie, patients can be counted in several categories for the same medication).

Prior medications, concomitant medications, and post-treatment medications are defined below and will be applied in the respective treatment periods (DBTP and SBTP).

• Prior medications are defined as medications for which the stop date is before the date of the first DBTP study treatment administration.

- Concomitant medications are defined as medications that are administered to the patients during the respective double-blind and single-blind study treatment periods. Specifically:
  - Start date of the concomitant medication is on or after the first study treatment administration in respective study treatment periods (≥ Day 1 for DBTP, or ≥ Day of the first single-blind study treatment administration for SBTP); or

Protocol: R4461-PLD-20100

Date: May 16, 2024

- Start date of the concomitant medication is before the first study treatment administration in respective study treatment periods and is "Ongoing" during the treatment emergent period; or
- Start date of the concomitant medication is before the first study treatment administration in respective study treatment periods, and the end date is on or after the first study treatment administration in respective study treatment periods (≥ Day 1 for DBTP, or ≥ Day of the first single-blind study treatment administration for SBTP).

The concomitant medication treatment emergent periods are defined as:

- For concomitant medications in DBTP, the double-blind treatment emergent period is defined from the day of the first double-blind study treatment administration to (1) the last day of double-blind study treatment + 112 days (for patients who do not continue into the SBTP); (2) to the day of the first single-blind study treatment administration (for patients who enter the SBTP).
- For concomitant medications in SBTP, the single-blind treatment emergent period is defined from the day of the first single-blind study treatment administration to the last day of single-blind study treatment administration + 112 days.

Note: In the case that the medication start day is before first study treatment administration and both ongoing status and stop date are missing, the medication will be assumed to be concomitant.

• Post-treatment medications are defined as medications for which the start date is after last date of study treatment administration + 112 days (≥ last study treatment +112 days).

# 4.4. Prohibited Medications and Procedures During Study

The definitions of prohibited medications and procedures are described in the Section 8.10.1 of the protocol. They will be reviewed and identified by the study clinician and reported in protocol deviations.

# 4.5. Patient Disposition

Patient disposition will include the description of patient status at major milestone decisions in the study, as well as the patient analysis populations.

For patient study status, patient milestone categories for the DBTP are defined below. As applicable, percentages will be calculated using the number of randomized patients in the

Regeneron Pharmaceuticals, Inc.

Page 21 of 88

denominator, with two exceptions. Specifically, the two exceptions will be for the screened and non-randomized categories, which will not have associated percentages shown.

- The total number of screened patients defined as having signed ICF.
- The total number of screen failure (SF) patients.
- The total number of randomized patients, defined as all screened patients with a double-blind treatment kit number allocated and recorded in the IVRS database, regardless of whether the treatment kit was used.
- The total number of patients randomized but not receiving study treatment.
- The total number of patients randomized and receiving study treatment.
- The total number of patients who completed the DBTP, defined as at least 11 weeks of study treatment administration and week 12 visit performed.
- The total number of patients who prematurely discontinued study treatment during the DBTP and the reasons for discontinuation collected on the study completion eCRF.
- The total number of patients who do not proceed into SBTP and complete the last study follow-up visit (ie, 16-week follow-up period).

Patient SBTP milestone categories are defined below. As applicable, percentages will be calculated using a denominator of the number of patients administered single-blind study treatment.

- The total number of patients receiving study treatment in single-blind treatment period
- The total number of patients ongoing in SBTP (applicable for first-step analysis)
- The total number of patients who completed the SBTP, defined as at least 23 weeks of study treatment administration and week 24 visit performed.
- The total number of patients who prematurely discontinued study treatment during the SBTP, and the reasons for discontinuation collected on the study completion eCRF.
- The total number of patients from SBTP who complete the last study follow-up visit (ie, 16-week follow-up period).

The following patient populations for analyses are defined in Section 3:

- Efficacy population: Full analysis set (FAS)
- Double-blind safety analysis set (DB SAF)
- Single-blind safety analysis set (SB SAF)
- Pharmacokinetic (PK) Analysis Set
- Immunogenicity (ADA) Analysis Set

Protocol: R4461-PLD-20100

The following patient listings will provide the details from the patient disposition table.

• A listing of patients treated but not randomized, patients randomized but not treated, and patients randomized but not treated as randomized

Protocol: R4461-PLD-20100

Date: May 16, 2024

• A listing of patient prematurely discontinued from treatment, along with reasons for discontinuation

# 4.6. Study Treatment Exposure and Compliance Variables

Study treatment exposure variables for study drug administered during the DBTP are listed below with associated definitions:

- Patient duration of DBTP SC study treatment exposure in weeks defined as: (last double-blind SC study treatment administration date first double-blind SC study treatment administration date+7)/7. Values will be rounded to one decimal place.
- The total number of DBTP SC study treatment injections by patient.
- The following categories will be used for DBTP SC treatment exposure at 1-week intervals: ≥1 day and <1 week, ≥1 week and <2 weeks, ≥2 weeks and <3 weeks, ≥3 weeks and <4 weeks, ..., ≥10 weeks and <11 weeks, ≥11 weeks.
- The total number of DBTP IV study treatment administrations by patient.

Study treatment exposure variables for study drug administered during the SBTP are listed below with associated definitions:

- Patient duration of SBTP SC study treatment exposure in weeks defined as: (last single-blind SC treatment administration date first single-blind SC treatment administration date+7)/7. Values will be rounded to one decimal place.
- The total number of SBTP SC study treatment injections by patient.
- The following categories will be used for SBTP SC treatment exposure at 1-week intervals: ≥1 day and <1 weeks, ≥1 weeks and <2 weeks, ≥2 weeks and <3 weeks, ≥3 weeks and <4 weeks, ..., ≥22weeks and <23 weeks, ≥23 weeks.
- The total number of SBTP IV study treatment administrations by patient.

Cumulative study treatment exposure variables combining DBTP and SBTP are listed below for all patients who received mibavademab in the DBTP:

- Cumulative patient duration of SC study treatment exposure in weeks defined as: DBTP SC treatment exposure + SBTP SC exposure.
- Cumulative total number of SC treatment administration by patient defined as: DBTP SC injections + SBTP SC injections.
- The following categories will be used for cumulative patient mibavademab treatment exposure in the study at 1-week intervals: ≥1 day and <1 weeks, ≥1 weeks and <2 weeks, ≥2 weeks and <3 weeks, ≥3 weeks and <4 weeks, ..., ≥22 weeks and <23 weeks, ≥23 weeks.
- The total number of DBTP and SBTP IV study treatment administrations by patient.

Regeneron Pharmaceuticals, Inc.

Page 23 of 88

With respect to patient treatment administration compliance, because the study treatment is administered either during the investigative site visits or by a visiting nurse, study compliance will be accessed by frequency for study drug administration for respective treatment periods (DBTP, SBTP), specifically:

- The administration frequency for DBTP SC study treatment administration will be defined for each patient as the average number of days between 2 consecutive SC study drug administration during DBTP: (last double-blind SC administration date first double-blind SC administration date) / (number of SC administrations during DBTP), for patients receiving at least 2 SC administrations during DBTP.
- The administration frequency for SBTP SC study treatment administration will be defined for each patient as the average number of days between 2 consecutive SC study drug administration during SBTP: (last single-blind SC administration date first single-blind SC administration date) / (number of SC administrations during SBTP), for patients receiving at least 2 SC administrations during SBTP.

In the DBTP, all important and minor protocol deviations potentially impacting efficacy analyses, randomization, and drug-dispensing irregularities, as well as other deviations, will be collected and reviewed on an ongoing basis throughout the study as described in the Protocol Deviation Plan (PDP). Both monitoring collected and programmatically derived deviations are listed and defined in the PDP.

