Baseline testing occurs in the screening period and the placebo run-in period (see Table 1). After baseline testing, patients in each cohort will be randomized 1:1 to study arm 1 (placebo in TP1 and REGN4461 in TP2) or study arm 2 (REGN4461 in TP1 and TP2), and stratified based on screening HbA1c (HbA1c \leq 7.0% or HbA1c \geq 7.0%) within each cohort.

On day 1, the first dose will be administered IV (mg/kg REGN4461 or placebo) and patients will be observed for at least 4 hours. Starting on day 8, patients will receive matched volumes of SC administered REGN4461 (mg QW) or placebo, respectively, once weekly for a total of 11 SC doses. Fasting blood draws will be taken every 2 weeks according to Table 2.

During the final 2 weeks of TP1, fasting blood draws will be performed weekly (weeks 10, 11, 12). The mean (geometric for TG and arithmetic for all other measures) of these 3 measurements will be taken as the end measure of TP1 and beginning measurement for TP2. Bioimpedance will be assessed during a mandatory in-clinic study visit (week 12). At the end of TP1, patients will undergo liver MRI and whole-body DXA.

12-week single-blind treatment period (TP2); Day 85 until week 24

On day 85 (week 12), patients will receive double-blind dosing in order to maintain blinding to study arm assignment and will then be observed for at least 4 hours:

- Study arm 1: IV loading dose of REGN4461 (mg/kg) followed by SC placebo;
- Study arm 2: placebo IV infusion followed by SC REGN4461 (mg).

Starting at week 13, REGN4461 (mg SC QW) will be administered in a single-blind manner to patients in both study arms (patient remains blinded to treatment allocation). Fasting TG and glucose measurements will occur every 2 weeks through week 20 (Table 2). During the final 2 weeks of TP2, fasting blood draws will be performed weekly (weeks 22, 23, 24). The mean (geometric for TG and arithmetic for all other measures) of these 3 measurements will be taken as the end measure of TP2. Bioimpedance will be assessed during the mandatory in-clinic visit (week 24). At week 24, patients will undergo liver MRI and whole-body DXA.

16-week off-drug safety follow-up period; Day 169 until week 40

This period will be used to monitor efficacy (glycemic, lipid parameters, daily lipodystrophy hunger patient reported outcome [PRO]), safety (hematology, chemistry, urinalysis, vital signs and AEs), PK and PD assessments as REGN4461serum concentrations decline.

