8. STUDY TREATMENTS

8.1. Investigational and Reference Treatments

The REGN4461 dose regimen for this study is mg/kg IV followed by doses of mg SC QW. Placebo product to match to REGN4461 is prepared in the same formulation without the addition of REGN4461. All administration of REGN4461 or placebo is to be performed by study staff and no self-administration of REGN4461 or placebo will occur.

Dosing Schedule:

• **Single-blind run in:** all patients will receive an IV placebo infusion on day -28, followed by placebo SC QW injections administered subsequently for 3 weeks starting on day -21.

• Treatment period 1:

- Study arm 1: IV placebo infusion on day 1 followed by SC QW injections of placebo for 11 weeks starting on day 8
- Study arm 2: IV REGN4461 (mg/kg) infusion on day 1 followed by SC injections of REGN4461 (mg QW) for 11 weeks starting on day 8

• Treatment Period 2:

- Study arm 1: IV REGN4461 (mg/kg) infusion followed by SC placebo on day 85, followed by SC injections of REGN4461 (mg QW) for 11 weeks starting on day 92
- Study arm 2: IV placebo followed by SC injection of REGN4461 (mg mg) on day 85, followed by SC injections of REGN4461 (mg QW) for 11 weeks starting on day 92

Investigational drug formulation and instructions on dose preparation are provided in the pharmacy manual for in-clinic visits and in the nursing manual for remote visits.

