**Table 1: Summary of Study Arms** 

		Arm 1	Arm 2	
Double- blind	Day 1 (IV loading dose based on weight)	Placebo IV	mg/kg mibavademab IV	
Treatment Period (DBTP)	Day 8 onwards (for 11 weekly maintenance doses)	Placebo SC QW	mg mibavademab SC QW	
Single- blind Treatment Period (SBTP)	Day 85 (IV loading dose based on weight)	■ mg/kg mibavademab IV followed by Placebo SC	Placebo IV followed by mg mibavademab SC	
	Day 92 (for 11 weekly doses)	mg mibavademab SC QW		
	Day 169 until week 40	Off-Drug Safety Follow-up		

The study event table is presented in Appendix 10.7.

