# **5.6.** Extent of Study Treatment Exposure and Compliance

The extent of study treatment exposure and compliance for the DBTP described in Section 4.6 will be assessed and summarized by treatment group, for patients in the DB SAF. The extent of study treatment exposure for the SBTP described in Section 4.6 will be assessed and summarized for all patients and by DB treatment group for patients in the SB SAF.

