## **5.6.2.** Study Treatment Compliance

The SC treatment compliance will be assessed by SC administration frequency for a treatment period (DBTP, SBTP), which is defined for each patient as the average number of days between 2 consecutive SC administrations during the treatment period: (last SC administration date – first SC administration date) / (total number of SC administrations during the treatment period - 1), for participants receiving at least 2 SC administrations during the treatment period.

Descriptive statistics of the SC administration frequency will be summarized separately for DBTP and SBTP by mean, SD, median, minimum, and maximum. Further, study treatment injection interruptions and incomplete injections with reason will be provided in a patient listing for those patients with incomplete injections.

Regeneron Pharmaceuticals, Inc.

Page 33 of 88

Protocol: R4461-PLD-20100

Important protocol deviations will be summarized. Both monitored and derived protocol deviations will be summarized for important deviation categories by count (percentage), and again by type of important deviation (patient count and percentage).

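### SAP 4.6 and SAP 5.6.2 give different divisors for the same SC administration-frequency variable, and the one in 4.6 does not yield the mean dosing interval

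*SAP*

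**What the plan says.** SAP 4.6 explains that, because staff give every dose, compliance will be judged from how often drug is administered. For the double-blind period (DBTP) it describes the variable as "the average number of days between 2 consecutive SC study drug administration during DBTP". The formula that follows takes the time from first to last SC dose and divides it by "number of SC administrations during DBTP), for patients receiving at least 2 SC administrations during DBTP". The bullet for the single-blind period (SBTP) has the same structure, with divisor "number of SC administrations during SBTP), for patients receiving at least 2 SC administrations during SBTP".

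SAP 5.6.2 defines the same variable for either period, with the same verbal description and the same minimum of two doses, but divides by "total number of SC administrations during the treatment period - 1". It then lists the descriptive statistics to be reported.

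SAP 5.6, the parent section of 5.6.2, points back to the earlier definition: "The extent of study treatment exposure and compliance for the DBTP described in Section 4.6 will be assessed". No statement says which of the two formulas governs.

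**The concern.** A mean interval is the total elapsed time divided by the number of intervals, and n doses enclose n-1 intervals. The 4.6 formula divides by n, so it cannot return the quantity that its own sentence defines. The 5.6.2 formula can. A programmer deriving the variable from the variable-definition section and one working from the methods section would report different numbers for the same patient.

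At stake is how the compliance table reads. The regimen is weekly, so a reader will compare the result with 7 days. Under 4.6, a fully compliant group would appear to be dosed more often than weekly, and one particular pattern of missed dosing would land exactly on 7.

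**Working it through.** The documents give no numerical value for this variable, so there is no stated figure to reproduce. The check applies both formulas to the planned dosing days.

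**Inputs**
- DBTP: Protocol 6.1 plans SC dosing "once weekly for a total of 11 SC doses", and SAP Table 1 starts it at "Day 8 onwards (for 11 weekly maintenance doses". The doses fall on Days 8, 15, ..., 78, so n = 11 and the span is 78 - 8 = 70 days.
- SBTP: Protocol 8.1 gives each arm an SC injection "on day 85, followed by SC injections of REGN4461 (mg QW) for 11 weeks starting on day 92". In arm 1 the Day 85 injection is placebo. The doses fall on Days 85, 92, ..., 162, so n = 12 and the span is 162 - 85 = 77 days.

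**Formulas**
- SAP 4.6: (last date - first date) / n
- SAP 5.6.2: (last date - first date) / (n - 1)
- Ratio of the first to the second: (n - 1)/n

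**Results (days)**

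| Scenario | n | Span | SAP 4.6 | SAP 5.6.2 |
|---|---|---|---|---|
| DBTP, all doses | 11 | 70 | 70/11 = 6.36 | 70/10 = 7.00 |
| DBTP, one dose missed between first and last | 10 | 70 | 70/10 = 7.00 | 70/9 = 7.78 |
| DBTP, first or last dose missed | 10 | 63 | 63/10 = 6.30 | 63/9 = 7.00 |
| DBTP, two doses missed between first and last | 9 | 70 | 70/9 = 7.78 | 70/8 = 8.75 |
| SBTP, all doses | 12 | 77 | 77/12 = 6.42 | 77/11 = 7.00 |
| SBTP, one dose missed between first and last | 11 | 77 | 77/11 = 7.00 | 77/10 = 7.70 |
| SBTP, first or last dose missed | 11 | 70 | 70/11 = 6.36 | 70/10 = 7.00 |

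For a full course the shortfall under 4.6 is 1/11, about 9%, in the DBTP and 1/12, about 8%, in the SBTP. It grows as the course shortens. With doses exactly a week apart, 4.6 gives 7 × 5/6 = 5.83 for six doses, 7 × 2/3 = 4.67 for three and 7 × 1/2 = 3.5 for two; the true mean interval is 7.00 each time.

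The restriction to patients with at least two doses also fits n-1. That divisor needs it to avoid dividing by zero, and division by n does not.

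**The case against.** The strongest reply is that the SAP already contains the right formula. SAP 5.6.2 sits in the statistical methods, is complete, and says what will be reported, so a programmer may well use it. That stands as a limit on the claim. A reader might infer that the compliance statistic will be wrong for every patient, but this follows only if 4.6 is programmed, and no document says so. It does not remove the point, because SAP 5.6 refers to 4.6 for DBTP compliance and leaves the choice open.

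A reader might also infer that under-dosing generally looks like good adherence under 4.6. The table does not support that. The score of 7.00 needs exactly one missed dose, lying between the first and last doses given (9 of the 11 DBTP positions). Missing the first or last dose moves the score further below 7, and two missed doses in between move it above 7.

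A third tempting reading ties this to the systemic dosing error for which SAP 5.7.1.1 plans a sensitivity analysis. That section does not describe the error or say that affected patients are identified from administration frequency. An average gap between injections would not detect a wrong amount per injection.

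Missed doses will also be visible elsewhere. SAP 4.6 and 5.6.1 report total injections and the number of patients treated at each weekly visit. SAP 5.6.2 adds a listing of interrupted and incomplete injections and a summary of important protocol deviations. SAP 5.8.8 still gives actual over planned injections as a percentage, although SAP 1.2.4 says that measure was replaced. Even the correct formula returns 7.00 when the first or last dose is missed, so mean interval is not a measure of dose completeness under either divisor. All of this limits the consequence but leaves the contradiction in place.

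Last, the minus sign between the two dates is missing from the 4.6 formulas in the extracted text, so symbols were lost there. For the divisor to be an extraction fault, the digit 1 would also have to be lost, in both bullets. That is unlikely, and a glance at the source file would settle it.

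**Conclusion.** The SAP contradicts itself on a reported variable, and the 4.6 formula is wrong as written because it does not compute the average it defines. If 4.6 is programmed, every value is (n-1)/n of the true mean interval, which puts full weekly dosing about 0.6 of a day below 7 in both periods. If 5.6.2 is programmed, the values are correct.

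The figures assume dosing on the planned days. The SBTP figures also assume that the Day 85 SC injection counts as an SBTP dose. If it did not, the SBTP course would be 11 doses from Day 92 to Day 162 and its values would equal those of the DBTP.

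The point is minor. The variable is summarised descriptively, no compliance threshold is applied to it, and no analysis set or efficacy analysis uses it.

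**What to change.** In both administration-frequency bullets of SAP 4.6 (DBTP and SBTP), replace the divisor with the number of SC administrations in that period minus 1, matching SAP 5.6.2. Alternatively, state the formula once and have the other section refer to it. The cost is a small text edit in two places, with no new data, no additional analysis and no change to any efficacy result. If the variable has already been programmed, confirm which divisor the code uses.
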